6.4.3.3 Safety/Pregnancy-related policy

The study PD/PI ([name]) will be informed of and review any potential Adverse Events. The DSMB will review all Adverse Event Reports and other interim safety data and will provide a report to the local IRB in compliance with local standards. If a participant develops a serious adverse event, the safety of continuing the intervention will be ascertained by the participant's obstetric care provider in collaboration with the site PI.

Maternal and perinatal morbidity outcomes are pre-specified secondary outcomes and will be statistically compared between intervention groups to assess for any signal of safety concerns.

6.4.3.4 Analysis of Subject Characteristics

Descriptive statistics including frequencies, percentages, means (+/- standard deviations) and medians (interquartile ranges) will be obtained. Baseline univariate and bivariate analyses will be performed using Fisher's exact tests and Chi-squared tests for categorical

variables and Student t-tests and Mann-Whitney U tests as appropriate based on the normality of the data.

6.4.3.5 Interim Analysis (if applicable)

Not applicable

6.4.3.6 Health economic evaluation

To estimate difference in cost and difference in quality adjusted life years (QALY) between the intervention and comparator groups, we will use a generalized linear model (GLM) with log link and gamma distribution for cost (given skewness in cost data) and identity link and normal distribution for QALY. Explanatory variable will be an indicator for intervention (vs. comparator) group. All analyses will follow the intention to treat principle. As randomization will be stratified by study site and amniotic membrane status, we will test if they are associated with cost or QALY and decide whether to include them as covariates in analysis. Cost-effectiveness will be evaluated by calculating the incremental cost effectiveness ratio (ICER), defined as $\Delta C/\Delta E$ where ΔC denotes the estimated difference in cost between the intervention and comparator groups and ΔE reflects the estimated difference in QALY between the two groups. ICER informs the additional cost associated with the intervention for each additional QALY gained. We will use non-parametric bootstrap resampling to estimate 95% CI of ICER and produce a cost-effectiveness plane and cost-effectiveness acceptability curve. In special situations where the intervention leads to significantly lower cost and higher QALY, the intervention is considered the dominant strategy. In situations where there is no significant difference in QALY between the two groups, a comparison of cost will inform the cost-effectiveness of the intervention; and vice versa. Our primary cost-effectiveness analysis will examine costs and health effects up to 2 weeks postpartum. We will also conduct two secondary analyses by: 1) extending the time period to 6 months postpartum, and 2) calculating QALY using participants' EuroQol five dimensions (EQ-5D) visual analogue scale (VAS) rating as a utility score (with linear transformation to a 0 to 1 scale).

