practices/institutions. For the assessment of maximal newborn weight loss, it is standard hospital practice at study sites to regularly weigh each newborn during their birth hospitalization. Infants are weighed naked using a digital scale, and the weight is expressed in kilograms. At the study site, newborns are weighed at birth and then at least daily until day of discharge. The first weight measured after birth is usually performed after at least 6 hours post-birth. Weighing is typically discontinued if the newborn regains his or her birth weight prior to discharge. Infant birth weights are recorded in a standardized fashion in specific EMR flowsheets at study sites. The date and time of each weight are recorded which allows calculation of precise age.

- The following cost outcomes will be assessed: 1) cost of relevant care, and 2) health-related quality of life. Both outcomes will be measured for the mother-infant pair.
 - **Cost of care** will include direct medical cost, direct non-medical care, and indirect cost. Direct medical cost will encompass hospital facility costs and provider professional fees associated with relevant care (maternal labor and delivery hospitalization, newborn's initial birth hospitalization, and infant's postnatal pediatric visits). Direct non-medical cost will account for breast pump use at home, infant formula use, and transportation to relevant care. Indirect cost (i.e., maternal productivity loss) will measure participants' work loss in the postpartum period. As the project will span multiple years, we will use consumer price index to inflation adjust all cost estimates to a constant year U.S. dollars

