Subjects will be administered study questionnaires at multiple timepoints, as outlined below. Questionnaires will be administered using the REDCap Survey tool, and electronic QR codes will be provided to the subjects via email or text message (whichever the subject prefers). Paper versions will also be available if requested.

After randomization, subjects will be asked to complete four questionnaires to establish baseline: the visual analog pain scale (28), the Edinburgh Postnatal Depression Scale (EPDS) (32), the Infant Feeding Intention Scale (IFI) (39), and the EQ-5D survey (41). Two hours after initiation of study intervention, subjects will again be asked to complete the visual analog pain scale (28) to assess their pain after intervention start.

During their hospital postpartum stay prior to discharge, subjects will be asked to complete three questionnaires: the visual analog pain scale (28) to rate their pain experienced during childbirth; the Labour Agency scale (29) to assess their feelings of control during childbirth; and the Birth Satisfaction Scale-Revised (BSS-R) (30) (31) to rate their satisfaction with the childbirth process. They will also be asked about whether they plan to attempt to breastfeed their infant. They will also be asked if they had any intrapartum expression of colostrum or breast milk, the quantity (mL or ounces) expressed if known, whether they collected and stored it for their baby, and whether they fed it to their baby.

After hospital discharge (preferably two weeks postpartum, but up to three weeks postpartum will be acceptable), all subjects, regardless of study group, will be asked to complete one questionnaire: the Perception of Milk Supply (40). The unique QR code or link to this electronic survey will be emailed or texted to the subject based on their preference. Follow-up phone call will be made if needed.

After hospital discharge (preferably six to eight weeks postpartum, but anytime within the window of four to twelve weeks postpartum will be acceptable), all subjects, regardless of study group, will be contacted to ask about any unanticipated outpatient or inpatient visits for them or their infants since discharge. Subjects will also be asked to complete two questionnaires: the Maternal Breastfeeding Evaluation Scale (33) and the EPDS (32).

After hospital discharge (6 months postpartum), all subjects will be asked to complete one questionnaire to assess infant feeding method.

Biospecimen Procedures:

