6.3.1 Study Schedule

There will be five expected study visits or encounters:

Study Encounter #1	
 • Screening and consent • Enrollment and randomization • Assess subject's baseline pain level using visual analog scale • Administer Edinburgh Postnatal Depression Scale to establish baseline • Administer Infant Feeding Intention Survey to establish baseline • Administer EQ-5D questionnaire to establish baseline • Initiation of assigned intervention • Assess subject's pain level two hours after intervention start using visual analog scale • Plasma and urine samples will be collected at Yale site • Milk samples will be collected 	During hospitalization for induction of labor
Study Encounter #2	
 • Assess subject's pain experienced during childbirth with visual analog scale • Administer Labour Agency questionnaire • Administer Birth Satisfaction Scale-Revised questionnaire • Administer EQ-5D[™] questionnaire • Administer EQ-TIPS[™] questionnaire • Milk samples will be collected up to twice a day (if applicable) postpartum 	During hospital postpartum stay prior to discharge
Study Encounter #3	
 • Administer PIMS questionnaire • Administer EQ-5D[™] questionnaire • Administer EQ-TIPS[™] questionnaire 	Contacted by email or text message 2 weeks postpartum

Study Encounter #4	
 • Administer Maternal Breastfeeding Evaluation Scale (MBES) questionnaire to all subjects who report at least one attempt at breastfeeding during the postpartum period. • Administer Edinburgh Postnatal Depression Scale questionnaire • Administer EQ-5D[™] questionnaire • Administer EQ-TIPS[™] questionnaire 	Contacted by email or text message 4-12 weeks postpartum
Study Encounter #5	
 • Administer short questionnaire to assess infant feeding method • Administer EQ-5D[™] questionnaire • Administer EQ-TIPS[™] questionnaire 	Contacted by email or text message 6 months postpartum

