2) The sample size of 988 for the primary outcome will be sufficient to detect a 9.4% or 10.8% absolute difference in breastfeeding as the sole source of nutrition (BSSN) at the time of delivery hospitalization postpartum discharge with 80% power and 90% power, respectively (two-sided test, $\alpha=0.05$). This represents the difference between an expected BSSN rate of 47% in the setting of synthetic oxytocin infusion without nipple stimulation (average rate at the study sites based on institutional data) and 56.4% (with 80% power) or 57.8% (with 90% power) with nipple stimulation therapy.

3) Assuming a 15% attrition rate at 2 weeks postpartum (the time frame for our primary cost-effectiveness analysis in Aim 3), the sample size of 988 will have 90% power for detecting a standardized effect size of 0.22 for the between-group difference in cost and difference in quality adjusted life years (QALY) (two-sided test, $\alpha=0.05$). This is considered a small effect size based on conventional criteria, hence if we observe an even larger effect size, we should be sufficiently powered.

The sample size for this biospecimen trial is based on the primary comparison, specifically the difference in primary biomarkers from baseline to after 2 hours of treatment between patients performing nipple stimulation therapy and those receiving IV oxytocin. Sample size calculations are based on differences between non-laboring and laboring patients from prior reports (Table). Sample size was determined to achieve 80% power to detect a difference with a two-tailed alpha level of 0.05. The final sample size of 48 per exposure group is based on the largest sample size required (IL1beta). Therefore, there is more than adequate power for the remainder of the biomarkers of interest.

To detect a 10 mM difference in sodium concentration between the intrapartum nipple stimulation therapy group and the immediate synthetic oxytocin infusion group at 48 hours postpartum, with a standard deviation of 20 mM, 80% power, and a significance level of 0.05, a sample size of 32 participants per group is required. Accounting for an expected 30% dropout rate, we plan to recruit 46 participants per group.

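### The QALY model omits the maternal baseline EQ-5D that the trial collects, and admits the randomisation strata only after a data-driven test

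*Protocol*

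**What the plan says.** Section 6.4.3.6 of the protocol gives the form of the QALY model, a generalized linear model with "identity link and normal distribution for QALY", which is an ordinary linear model. It then gives the content: "Explanatory variable will be an indicator for intervention (vs. comparator) group". Site and membrane status, which section 6.1.2 names as the stratification factors, are treated as candidates: "we will test if they are associated with cost or QALY and decide whether to include them as covariates in analysis". Baseline EQ-5D is not named as a covariate there or anywhere else in the protocol.

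The measurement is nevertheless taken. The first encounter in section 6.3.1 includes "Administer EQ-5D questionnaire to establish baseline", listed ahead of the start of the assigned intervention. Section 6.3 places it in time: "After randomization, subjects will be asked to complete four questionnaires to establish baseline", and EQ-5D is one of the four.

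Three other statements bear on the point. Section 5.2.2 says of cost and quality of life: "Both outcomes will be measured for the mother-infant pair". Section 6.4.3.6 sets the horizon: "Our primary cost-effectiveness analysis will examine costs and health effects up to 2 weeks postpartum". Section 6.4.2 claims "90% power for detecting a standardized effect size of 0.22", on 988 participants with 15% attrition and a two-sided 5% test.

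**The concern.** When a baseline value of the outcome measure is available, a linear model that leaves it out gives up whatever precision it would have bought. A chance difference in baseline utility between the arms also stays inside the estimated QALY difference. From there it passes into the denominator of the ICER, the bootstrap interval and the acceptability curve.

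The QALY test also steers the conclusion. Under section 6.4.3.6, dominance requires significantly lower cost and higher QALY, and if QALY does not differ significantly, the comparison of cost informs the conclusion. The precision of the QALY estimate therefore affects which reading of cost-effectiveness is reported.

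The test for site and membrane status is a separate weakness. Randomisation is stratified on these factors, so the analysis should carry them whatever the data show. Letting a test decide makes the primary economic model depend on the data. It also leaves open whether the choice is repeated in each bootstrap sample; if it is made once and then held, the interval ignores the selection step.

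**Working it through.** **Inputs.** From section 6.4.2: N = 988, attrition 15%, standardized effect 0.22, two-sided alpha 0.05, power 90%. From section 6.1.2: 1:1 allocation. The correlation ρ between maternal baseline EQ-5D utility and the QALY outcome is not in the protocol; 0.1, 0.3 and 0.5 are assumed to show a range.

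**1. The plan's own figure.**
- Evaluable per arm: 988 × 0.85 / 2 = 419.9, taken as 420.
- SE of a standardized difference: √(2/420) = 0.0690.
- Effect detectable with 90% power: (1.960 + 1.282) × 0.0690 = 0.224, which rounds to the stated 0.22.
- Power at exactly 0.22: Φ(0.22/0.0690 − 1.960) = 89.0%. A noncentral t calculation also gives 89.0%.

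The stated figure is reproduced by an unadjusted comparison of two means.

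**2. Effect of adjusting for baseline.** The residual SD becomes √(1 − ρ²), so variance falls by ρ² and the SE becomes 0.0690 × √(1 − ρ²). The gain expressed as extra participants is 1/(1 − ρ²) − 1.

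| Assumed ρ | Variance reduction | Equivalent extra participants | Effect detectable at 90% | Power at 0.22 |
|---|---|---|---|---|
| none (unadjusted) | – | – | 0.224 | 89.0% |
| 0.1 | 1% | 1% | 0.223 | 89.3% |
| 0.3 | 9% | 10% | 0.213 | 91.7% |
| 0.5 | 25% | 33% | 0.194 | 95.7% |

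**3. Chance imbalance.** The baseline difference between arms has SE 0.0690 SD, so its 95% chance limit is 1.96 × 0.0690 = 0.135 SD. An imbalance of that size moves the unadjusted QALY difference by ρ × 0.135 SD.

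| Assumed ρ | Shift in QALY difference | Share of 0.22 SD |
|---|---|---|
| 0.1 | 0.014 SD | 6% |
| 0.3 | 0.041 SD | 18% |
| 0.5 | 0.068 SD | 31% |

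**4. Does another section supply the adjustment?** Section 6.4.4 allows adjusted analyses as needed. It calls them exploratory, names Poisson and quantile regression, and mentions neither QALY nor EQ-5D. The biomarker plan in section 6.4.3.2 does use the baseline value as a covariate in a supportive analysis, but the QALY model has no counterpart.

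**The case against.** The strongest reply is that nothing here is invalid. The unadjusted difference is unbiased over randomisation, the power claim holds without covariates, and the outcome belongs to a secondary objective. All of that stands.

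The benefit may also be small. Baseline is taken during admission for induction, while the outcome runs to 2 weeks postpartum. It covers the pair, and the infant part, measured by a separate proxy instrument, can have no baseline. A correlation near 0.1 is possible, and the gain would then be negligible. This stands as a limit on the size.

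Nor is the baseline cleanly pre-treatment. It is self-reported after randomisation in an open-label trial, so knowledge of the assignment could colour it, and adjustment could then carry that influence into the estimate. This also stands, and wording alone cannot cure it for women already enrolled: section 5.1.1 expects enrolment from October 2021 to June 2026, and this protocol version is dated July 2025.

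Finally, a covariate list can be left to a statistical analysis plan, which is not at hand. That reply is weaker, because section 6.4.3.6 is not silent: it states the distribution, the link, the explanatory variable and the rule for admitting others.

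A reader might infer three stronger things that the protocol does not support:
- **That the 90% power is missed.** The gap between 89.0% and 90% comes from printing 0.224 as 0.22.
- **That an imbalance could be as large as the effect, because QALYs over 2 weeks are tiny (at most 14/365 = 0.038 per person).** A short horizon shrinks the effect, the SD and the imbalance together. Even at ρ = 0.5, matching 0.22 SD would need a baseline imbalance of 0.22/0.5 = 0.44 SD, more than six standard errors.
- **That the model can hold only the arm indicator.** Site and membrane status are admitted conditionally.

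**Conclusion.** The point holds as a weakness in efficiency and in protection against chance imbalance. It is not an error in any stated figure, and it does not bias the QALY difference over randomisation. The stated model omits a baseline measure of utility that the trial collects, and it makes the randomisation strata depend on a test of the data.

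The size cannot be settled from the protocol. It runs from negligible at a correlation of 0.1 to a saving worth a third more participants at 0.5. These figures assume 420 evaluable per arm, a linear relation between baseline utility and QALY, and a baseline unaffected by knowledge of the assignment. The case against pre-testing the strata does not depend on the correlation.

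The change is worth making before the data are analysed, because it costs little and the QALY test helps decide how cost-effectiveness is concluded.

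**What to change.** Replace the model sentence in section 6.4.3.6 with a pre-specified linear model for QALY containing arm, maternal baseline EQ-5D utility, study site and membrane status. Delete the test that decides whether the strata enter. Refit this model in each bootstrap replicate used for the ICER interval, the cost-effectiveness plane and the acceptability curve.

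State two limits beside it: only the mother has a baseline although the QALY covers the pair, and the baseline is completed after randomisation in an open-label trial. Because of these, report the model with arm, site and membrane status but without baseline EQ-5D as a sensitivity analysis. For remaining participants, have the baseline form completed before the assignment is disclosed, where feasible.

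The analysis change costs a few sentences and needs no new data. The change in the order of the form is a procedural amendment, and it cannot repair baselines already taken.

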4.1 Hypothesis

Our central hypothesis is that nipple stimulation with an electronic breast pump to induce labor increases spontaneous vaginal delivery, shortens duration of labor induction, improves patient-reported pain scores during labor, improves patient satisfaction and sense of self agency with the birthing process, and improve scores on the postpartum depression scale. We also hypothesize that participants assigned to nipple stimulation therapy during labor will be more likely to use breastfeeding as the sole source of nutrition at hospital discharge, which will be associated with improved maternal perception of milk supply, less severe newborn weight loss, and sustained breastfeeding for the recommended 6 months. Secondly, we hypothesize that intrapartum nipple stimulation will not increase fetal or neonatal morbidity outcomes. Last, by examining cost of care and health-related quality of life, we hypothesize that performing nipple stimulation therapy during labor will be more cost-effective than the comparator after considering their overall impact on labor and delivery, breastfeeding, and early infant nutrition and care in the first 6 months.

We also hypothesize that nipple stimulation therapy invokes the wide cascade of events that promote labor to a greater extent than IV oxytocin alone. We hypothesize that oxytocin in the plasma of patients performing nipple stimulation will rise less than among subjects receiving IV oxytocin at the time when the subject is first contracting regularly. We hypothesize that other proteins associated with labor (including but not limited to IL6, IL1beta, plasminogen activator inhibitor 1, C reactive protein, ICOS ligand, and ERP29 will rise more in the circulation of subjects receiving nipple stimulation therapy compared with IV oxytocin. We hypothesize that urinary metabolites of prostaglandin E2 and F2alpha will be higher in subjects receiving nipple stimulation therapy. We hypothesize that, on a systematic level, plasma changes among subjects partaking in nipple stimulation will differ from subjects receiving IV oxytocin. We hypothesize that nipple stimulation therapy will have earlier secretory activation as measured by milk sodium and conductivity) in the early days postpartum, compared to individuals receiving IV oxytocin alone.

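### The planned bootstrap 95% CI of the ICER is a poor measure of uncertainty here: it cannot separate a dominant from a dominated result and is unstable when the QALY difference is near zero

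*Protocol*

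**What the plan says.** Protocol section 6.4.3.6 (Health economic evaluation) estimates ΔC with a gamma log-link GLM and ΔE with a normal identity-link GLM, and defines the ICER as ΔC/ΔE. It reads the ratio as follows: "ICER informs the additional cost associated with the intervention for each additional QALY gained". On uncertainty it says: "We will use non-parametric bootstrap resampling to estimate 95% CI of ICER and produce a cost-effectiveness plane and cost-effectiveness acceptability curve".

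Two rules in the same section work on the separate differences. The first is: "In special situations where the intervention leads to significantly lower cost and higher QALY, the intervention is considered the dominant strategy". The second is: "In situations where there is no significant difference in QALY between the two groups, a comparison of cost will inform the cost-effectiveness of the intervention". The reverse applies when cost does not differ.

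On the horizon: "Our primary cost-effectiveness analysis will examine costs and health effects up to 2 weeks postpartum". A 6-month horizon is a secondary analysis. Section 4.1 states the expected direction: "we hypothesize that performing nipple stimulation therapy during labor will be more cost-effective than the comparator".

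The section does not say how the ICER interval is formed or read when replicates are negative or when ΔE changes sign. It names no dominated case, no willingness-to-pay value and no net-benefit summary.

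**The concern.** A ratio of two differences keeps its sign when both differences change sign. Saving money while gaining QALYs and spending money while losing QALYs therefore produce the same negative ICER. Ranking replicates on that scale puts opposite conclusions side by side.

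Within the dominant quadrant the size of the ratio has no useful order either, because a larger QALY gain moves a negative ICER towards zero. When ΔE is close to zero, the ratio jumps between large negative and large positive values.

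This trial is likely to meet both problems. The hypothesis points to the negative-ICER quadrant, and two weeks leave little room for a QALY difference. At stake is the number that will be reported as the uncertainty of the primary cost-effectiveness result.

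**Working it through.** **Inputs from the protocol.** Total 988, randomised 1:1; 15% attrition at 2 weeks; standardized effect 0.22 for cost and for QALY with 90% power, two-sided 0.05 (section 6.4.2); utilities on a 0 to 1 scale (section 5.2.2); 2-week primary horizon (section 6.4.3.6).

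**Assumed, because the protocol gives none.** Cost SD 12,000 dollars, 2-week QALY SD 0.004, correlation -0.1, and a threshold λ of 100,000 dollars per QALY. A second set (cost SD 8,000, QALY SD 0.004, correlation 0) shows how far the dollar figures move.

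**1. The plan's own figure.** Per arm, 988 × 0.85 / 2 = 419.9. Detectable effect = (1.960 + 1.282) × √(2/419.9) = 0.224. Power at 0.22 is 0.890. The stated 0.22 is reproduced to within rounding, and nothing below changes it.

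**2. Sign of the ratio.** This step needs no SDs.
- Dominant: ΔC = -500, ΔE = +0.001. ICER = -500,000 per QALY. Net benefit λΔE - ΔC = 100 + 500 = +600.
- Dominated: ΔC = +500, ΔE = -0.001. ICER = -500,000 per QALY. Net benefit = -100 - 500 = -600.

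The ratio is identical and the net benefit is opposite.

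**3. Room for a QALY difference.** 14/365 = 0.038 QALY per person at most, or about 0.077 if mother and infant utilities are summed (an assumption).

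**4. Chance that the 95% interval for ΔE spans zero.** The standard error in SD units is √(2/420) = 0.0690. The chance is Φ(1.96 - d/0.0690) - Φ(-1.96 - d/0.0690).
- d = 0.10: about 70%.
- d = 0.22: about 11%.

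**5. Percentile interval of the ratio.** Bivariate normal draws of (ΔC, ΔE), with standard error SD × 0.0690, stand in for the bootstrap. Observed effects are in SD units. Values below use the first assumed set.

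| ΔC, ΔE | Main quadrant | 95% interval of ICER (million $/QALY) | P(net benefit > 0) |
|---|---|---|---|
| -0.22, +0.22 | 99.9% dominant | -8.1 to -1.1 | 0.999 |
| +0.22, -0.22 | 99.9% dominated | -8.1 to -1.1 | below 0.001 |
| -0.22, +0.10 | 93% dominant | -58 to +43 | 0.999 |
| +0.22, +0.22 | 99.9% dearer and better | +1.0 to +8.9 | 0.001 |

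For the first pair, the net-benefit intervals at λ = 100,000 are about +1,100 to +4,360 and -4,360 to -1,100 dollars. They are clearly opposite.

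With the second assumed set, the first pair gives -5.7 to -0.69 million for both members, and the third row gives about -40 to +30 million. The dollar limits move with the SDs, but the equality of the mirror intervals does not.

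**The case against.** The strongest reply is that the plan does not depend on this interval. The same sentence commits to a cost-effectiveness plane, which shows the quadrant of every replicate, and to an acceptability curve, which is the probability that net benefit is positive across thresholds. In the table that probability separates the mirror pair at 0.999 against less than 0.001. The section also judges dominance on ΔC and ΔE directly, and falls back on cost alone when QALYs do not differ significantly. Although no dominated case is named, the signs of the two estimates would reveal it.

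A reader might infer from the ratio's behaviour that the trial cannot tell which strategy is cost-effective, or that the hypothesis in section 4.1 cannot be answered. The documents do not support that, for the reasons just given.

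Other parts of the reply also stand:
- When nearly all replicates show higher cost and higher QALY, the interval is ordered and readable (last row of the table).
- At the planning effect of 0.22 SD, ΔE is clear of zero in about 89% of trials.
- The protocol does not say that replicates are ranked as raw ratios. An analysis plan not shown here could specify otherwise.
- The SDs are assumed, and normal draws replace a gamma model.
- Cost-effectiveness is a secondary objective.

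What the reply does not remove is the stated interval. Unless it is qualified, the same limits can be published for opposite findings. A clearly favourable result with a small QALY gain (third row) would carry an interval running from a large negative to a large positive number. The separate significance rules do not replace it either, because they ignore the joint uncertainty of cost and QALY.

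**Conclusion.** The point holds as a minor defect, confined to the reported ICER interval as the measure of uncertainty. Two parts of it do not depend on assumed SDs: a dominant result and its mirror-image dominated result give the same interval when replicates are ranked as ratios, and the ratio is unstable when ΔE is near zero. How often the second problem arises depends on the true QALY effect: about 70% of trials at 0.10 SD and about 11% at 0.22 SD would have a ΔE interval spanning zero. The dollar limits are illustrations only. The plane, the acceptability curve and the separate comparisons still show direction. No sample size, power figure or clinical outcome is affected.

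**What to change.** In section 6.4.3.6, make incremental net monetary benefit (λΔE - ΔC) with its bootstrap 95% CI, at pre-stated willingness-to-pay values, the measure of uncertainty. Present it beside the plane and acceptability curve already planned. Report an ICER with its CI only when essentially all replicates lie in one trade-off quadrant (ΔC and ΔE of the same sign) and ΔE is clearly away from zero. Otherwise, report the share of replicates in each of the four quadrants.

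The change takes a sentence or two and uses the same replicates, with no new data. The one cost is that the willingness-to-pay values must be chosen and stated in advance. Doing so before the data are seen also avoids choosing the summary afterwards.

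### The cost-effectiveness reading rule treats a non-significant QALY or cost difference as no difference, sets no equivalence margin, and names two deciders when neither is significant

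*Protocol*

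**What the plan says.** Protocol section 6.4.3.6 models cost and QALY separately and forms an ICER. It then plans the joint uncertainty without any condition: "We will use non-parametric bootstrap resampling to estimate 95% CI of ICER and produce a cost-effectiveness plane and cost-effectiveness acceptability curve".

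Two interpretation statements follow, and both depend on significance. The first concerns dominance: "In special situations where the intervention leads to significantly lower cost and higher QALY, the intervention is considered the dominant strategy". The second is the rule at issue: "In situations where there is no significant difference in QALY between the two groups, a comparison of cost will inform" how the result is read. The same sentence closes by adding the reverse case: "the cost-effectiveness of the intervention; and vice versa".

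The main horizon is short: "Our primary cost-effectiveness analysis will examine costs and health effects up to 2 weeks postpartum". One secondary analysis works by "extending the time period to 6 months postpartum".

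The only sizing for these endpoints is in section 6.4.2. "Assuming a 15% attrition rate at 2 weeks postpartum", it says that "the sample size of 988 will have 90% power for detecting a standardized effect size of 0.22 for the between-group difference in cost" and for the QALY difference (two-sided, alpha 0.05). This is a superiority calculation. No equivalence margin, minimal important difference or confidence-interval criterion is given for either quantity.

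**The concern.** A cost-only comparison is justified when health effects have been shown to be close enough to equal. A p-value above 0.05 does not show that. It may equally mean that the trial was too small to see a difference that matters in money. The reversed half has the same defect for cost.

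The sentence also fails on its own terms. If neither difference is significant, its first half sends the reader to cost and its second half to QALY. These can favour opposite arms, and either can disagree with the acceptability curve planned in the same section.

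At stake is the cost-effectiveness conclusion, which is a stated hypothesis (section 4.1) and a secondary objective (section 4.3). The primary outcome, the trial's sample size and safety are not affected.

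**Working it through.** **Step 1. The plan's own figure.** Section 6.4.2 gives 988 participants and 15% attrition; section 6.1.2 gives 1:1 allocation. Per arm n = 988 × 0.85 / 2 = 419.9. Detectable d = (1.960 + 1.282) × √(2/419.9) = 0.224. Power at d = 0.22 with 420 per arm is 0.89. The stated 0.22 at 90% power reproduces.

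**Step 2. How often a real difference is non-significant.** With z = d × √(420/2) = 14.49d, P(significant) = Φ(z − 1.96) + Φ(−z − 1.96).

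| True d | z | P(non-significant) |
|---|---|---|
| 0.05 | 0.72 | 89% |
| 0.10 | 1.45 | 69% |
| 0.15 | 2.17 | 42% |
| 0.20 | 2.90 | 17% |
| 0.22 | 3.19 | 11% |

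No assumption about SDs or willingness to pay is needed here.

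**Step 3. Neither significant.** With no true difference in cost or QALY and independent errors, the probability is 0.95 × 0.95 = 0.90. Under any dependence it is at least 1 − 0.05 − 0.05 = 0.90 and at most 0.95. In all these trials the sentence names two deciders.

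**Step 4. Dominance.** Suppose the intervention is truly better by 0.10 SD on both cost and QALY. If both must be significant, and errors are independent, it is called dominant in 0.305 × 0.305 = 9% of trials.

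**Step 5. Decision error at 6 months (assumed inputs).** The protocol gives no utility SD, cost SD, correlation, willingness to pay or 6-month attrition. Assume 420 per arm, utility SD 0.15, $100,000 per QALY, independent errors, 0.01 utility gained over half a year and $200 extra cost.

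- True net benefit = 100,000 × 0.005 − 200 = +$300.
- SE of the QALY difference = 0.15 × 0.5 × √(2/420) = 0.005175, worth $517.5.
- QALY z = 0.005/0.005175 = 0.97, so P(non-significant) = 0.84.
- SE of the cost difference = cost SD × 0.0690.

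Rule as coded: only cost significant, cost decides; only QALY significant, QALY decides; both or neither significant, net benefit decides. For net benefit alone, P(correct) = Φ(300 / √(517.5² + SE of cost²)). The rule's figures come from simulating independent normal estimates.

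| Cost SD | SE of cost | P(only cost significant) | Rule correct | Net benefit correct |
|---|---|---|---|---|
| $1,000 | $69 | 0.84 × 0.83 = 69% | 27% | Φ(300/522) = 72% |
| $3,000 | $207 | 0.84 × 0.16 = 14% | 65% | Φ(300/557) = 70% |
| $8,000 | $552 | 0.84 × 0.065 = 5% | 65% | Φ(300/757) = 65% |

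At $3,000 neither difference is significant in about 70% of trials (0.84 × 0.84). In 48% of all trials the two halves then point to opposite arms.

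**Step 6. The reversed half at 2 weeks (assumed inputs).** Two weeks is about 0.0383 years. With utility SD 0.20, a true gain of 0.22 SD is 0.044 × 0.0383 = 0.0017 QALY, worth $84, $169 or $253 at $50,000, $100,000 or $150,000 per QALY. With cost SD $8,000, a true extra cost of 0.10 SD is $800. True net benefit is therefore −$716, −$631 or −$547. QALY is significant and cost is not with probability 0.89 × 0.695 = 0.62, and the rule then favours the intervention. Net benefit would be wrong in about 10% to 16% of trials: Φ(−716/553) = 10%, Φ(−547/558) = 16%.

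**The case against.** The strongest objection is that the sentence says only that one comparison will inform the conclusion, while the ICER, its bootstrap interval, the plane and the acceptability curve are planned unconditionally. A reader might infer that the rule overrides those outputs or discards the joint uncertainty. The text does not say so; the joint evidence will be produced and can be reported. What remains is that this is the only stated guide to reading the result when significance is absent, and it can disagree with the curve beside it.

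The second objection concerns size, and it largely stands. A reader who lets cost decide whenever QALY is non-significant would find the rule correct in only 30% of trials in the $3,000 example. That applies half of the sentence and assigns every neither-significant trial to cost, which the text does not do. With both halves applied the gap is 65% against 70%. If QALY settles the undefined case, the rule scores 73% and beats net benefit.

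Nor is the rule worse in every setting. With 0.005 utility gained and $400 extra cost (true net benefit 250 − 400 = −$150; other inputs as in the $3,000 example), the same simulation gives 71% correct for the rule against Φ(150/557) = 61% for net benefit. The protocol also foresees possible cost savings (section 3.3.2), where cost and QALY would more often agree.

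Finally, willingness-to-pay values may sit in an analysis plan that is not shown, and their absence here is not the fault. The fault is a rule that the protocol itself fixes.

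**Conclusion.** The point holds as a fault in a stated interpretation rule. Non-significance cannot stand for equality at this sizing: differences of 0.10 and 0.15 SD are missed about 69% and 42% of the time. The sentence also gives no single answer in the neither-significant case, which covers at least 90% of trials if nothing truly differs. These figures rest only on the protocol's sample size, attrition and allocation, with a normal approximation.

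The effect on decisions is uncertain. In the assumed 6-month example it runs from a large loss (27% against 72% correct) through a small one (65% against 70%) to none as cost SD rises, with 420 per arm assumed to remain at 6 months. At the primary 2-week horizon the reversed half matters most, because a real cost difference can be set aside for a QALY gain worth little money. A reader might infer that the rule always misleads, or that it undermines the trial's main result; the documents support neither. The change should be made, but it concerns a secondary objective.

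**What to change.** In section 6.4.3.6, delete the sentence that switches to cost alone or QALY alone when the other is non-significant, and do not make dominance depend on separate p-values. State that the conclusion, whatever those p-values, rests on incremental net monetary benefit with a bootstrap 95% confidence interval and on the planned acceptability curve, over named willingness-to-pay values. Apply this at both 2 weeks and 6 months.

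If a cost-minimisation reading is wanted, pre-specify a QALY equivalence margin and require the confidence interval to lie within it before cost alone is compared.

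The cost is wording plus a trivial calculation from bootstrap replicates already planned. No new data or participants are needed. The one demand is that the team must state its willingness-to-pay values in advance.
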